### **10.4.3. Urine sample collection and analysis**

Urine samples for analysis of GSK2983559 and GSK2669176 as well as any metabolites will be collected at the time points listed in Section 2, SoA Table.

Prior to dosing on Day 1, each subject will be instructed to void their bladder and no more than 40 mL of this urine sample will be retained as a control. Urine collection time points listed in the SoA table will begin immediately following dose administration (0 to 24 hours). The time will be recorded for each urine sample collected as well as the 24-hour volume of urine for each subject. In Part A only, urine obtained at the highest dose reached will be shipped to GSK. Results will be reported under a separate PTS-Global Spectroscopy, GlaxoSmithKline protocol. Processing, storage and shipping procedures are provided in the Study Reference Manual (SRM).

### **10.5. Exploratory Pharmacodynamics and Target Engagement**

Blood samples will also be collected at the time points indicated in Section 2 SOA. The actual date and time of these collections will be recorded. All procedures will be performed at the site.

### **10.6. Pharmacodynamic Samples**

For this assay 1 mL of blood will be drawn into TruCulture tubes containing a standardized amount of the NOD2 agonist, MDP. Following a 6 hr incubation at 37°C, plasma cytokines (macrophage inflammatory protein 1 alpha [MIP1 $\alpha$ ], MIP1 $\beta$ , and TNF) will be quantified using the MesoScale Discovery platform. Two pre-dose baseline samples will be drawn to measure the maximum intrasubject inhibition via treatment with a tool compound with a similar chemical structure to GSK2983559. Details of the collection, processing, and storage of these PD samples are provided in the SRM.

### **10.7. Target Engagement (TE) Samples**

Two sets of samples will be used to evaluate target engagement. (1) For ex-vivo evaluation of TE, blood will be drawn into 2 mL sodium heparin or K2 EDTA tubes. (2) For post-challenge evaluation of TE, an aliquot of the residual cells will be collected from the Truculture PD samples (described above). Cellular lysates will be prepared from both sets of samples and TE will be assessed using a novel competitive binding assay. Details of the collection, processing and storage of these TE samples are provided in the SRM.

## **11. STATISTICAL CONSIDERATIONS**

The objectives of this study are to assess the safety and tolerability of single and repeat ascending doses of GSK2983559 in healthy volunteers. No formal hypotheses will be tested.

### **11.1. Sample Size Determination**

A minimum number of 18 participants (10 in cohort 1 and 8 in cohort 2) will be recruited into Part A, and up to 40 participants (10 in each of 4 cohorts) will be recruited into Part B. An additional cohort may be added to Part A of the study to allow for evaluation of additional dose levels or repeat an existing dose level.

The sample size is based on feasibility considerations and no statistical techniques were used to calculate it.

Safety is the primary objective of Parts A and B, where numbers of safety events are of interest.

A maximum of 9 participants will receive each of the active doses in Part A or B. If 0 out of 9 participants with a particular safety event is observed, there is 95% certainty that the probability of observing a participant on active with a particular safety event will lie between 0.04 and 0.39.

There is no sample size re-estimation planned.

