### Overall Design:

This study will be a randomised, double-blind (sponsor open), placebo-controlled, two-part study of oral administration of GSK2983559 in healthy participants. Part A will be a single ascending dose crossover design in two separate cohorts of participants (Cohorts 1 and 2). In addition to the crossover treatment periods, subjects in Cohort 2 will participate in an additional treatment period and receive open-label GSK2983559 under fed conditions. Part B will be a repeat dose design in up to 4 cohorts of participants (Cohorts 3-6). This study is planned to include approximately 62 participants.

Parts A and B of this study will be double-blind with respect to participants, investigator and site staff (except for the site pharmacist). Sponsor open refers only to members of the Dose Escalation Committee (DEC) at defined meetings. Members and requirements are provided in a Dose Escalation Charter.

- **Part A** – single ascending doses, randomized, placebo controlled, crossover.

Part A plans to explore up to 9 single ascending dose levels. This will be 2 cohorts, Cohort 1 (standard capsule) and Cohort 2 (enteric capsule), of 10 and 12 healthy participants, respectively. The total duration of Part A of the study for each participant, including screening and follow-up, is approximately 11 weeks.

- **Part B** – repeat ascending dose, randomized, placebo controlled, sequential-group.

Part B will consist of up to four cohorts of 10 healthy participants. The total duration of Part B of the study for each participant, including screening and follow-up, is approximately 15 weeks. The treatment period will be 14 days.

In all cases the decision to proceed to the next dose level will be made at a DEC meeting (see Study Governance Considerations).

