## 5.2. Number of Participants

Participants will be screened to ensure that a minimum of 62 are eligible to be randomised (10 participants into Cohort 1, 12 participants into Cohort 2, and 10 participants into each of Cohorts 3-6), so that a minimum of evaluable participants are achieved in each of cohorts as described in the table below:

		Randomised	Evaluable
Part A	Cohort 1 (single dose)	10	4 out of 8 on active
	Cohort 2 (single dose)	12	4 out of 9 on active
	Cohort 2 (food effect)	up to 12	4 out of at least 8 on active
Part B	Cohorts 3-6 (repeat dose)	10	4 out of 8 on active
	Total	62	

Participants are considered as evaluable if the following are completed:

- Part A - Cohort 1 (single dose): screening and all 5 treatment periods.
- Part A - Cohort 2 (single dose): screening and all 3 or 4 treatment periods.
- Part A - Cohort 2 (food effect): screening and all 2 treatment periods (fed and fasted).
- Part B - Cohort 3-6 (repeat dose): screening and the 14-day treatment period.

Additional participants/cohorts may be enrolled to allow for evaluation of additional dose levels. No more than 10 additional participants will be allowed in a cohort either in Part A and/or B. The schedule of assessments will be as for these parts and the number of dosing periods will not exceed those in the current cohorts.

If a participant withdraws prematurely from Part A of the study, additional participants may be recruited and assigned to the same treatment sequence, starting from the current dosing period of the early withdrawal at the discretion of the sponsor in consultation with the investigator.

If a participant withdraws prematurely from Part B of the study, additional participants may be recruited and assigned to the same repeat dose level, starting from baseline at the discretion of the sponsor in consultation with the investigator.

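### Section 11.1 gives an impossible 95% interval for 0 of 9 events (0.04 to 0.39; exact is 0 to 0.336) and still counts Cohort 2 as 8, not 12

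*Protocol*

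**What the plan says.** Protocol Section 11.1 makes three statements that matter here.

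- Precision: for 0 of 9 participants with an event, "there is 95% certainty that the probability of observing a participant on active with a particular safety event will lie between 0.04 and 0.39". No interval method is named.
- Number on active: "A maximum of 9 participants will receive each of the active doses in Part A or B".
- Part A size: "A minimum number of 18 participants (10 in cohort 1 and 8 in cohort 2) will be recruited into Part A".

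It also says that "The sample size is based on feasibility considerations and no statistical techniques were used to calculate it".

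Other current text gives a different Cohort 2. The synopsis and Section 5.1 describe "Cohort 1 (standard capsule) and Cohort 2 (enteric capsule), of 10 and 12 healthy participants, respectively". Section 5.2 says "Participants will be screened to ensure that a minimum of 62 are eligible to be randomised", made up of "10 participants into Cohort 1, 12 participants into Cohort 2, and 10 participants into each of Cohorts 3-6". Table 6 has four sequences of 3. The sentinel text in Section 5.1 has 2 participants dosed first and 10 remaining. The evaluability table in Section 5.2 shows 9 on active per Cohort 2 single dose and 8 in each other cohort. For the food-effect part it shows up to 12 participants, with "4 out of at least 8 on active" needed as evaluable.

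**The concern.** After zero events the data cannot exclude any rate close to zero, so a lower limit of 0.04 is suspect on sight. Taken literally, the sentence tells the reader that a dose group with no events supports a true rate of at least 4%. The upper limit also looks too large for 9 participants.

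The Cohort 2 count of 8 looks like text that the change to 12 did not reach. It disagrees with Section 5.2 and with the 9 on active given in the same section.

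Safety is the primary objective of both parts, and this is the only statement in either document of how precisely event rates can be known. Ethics committees, regulators and readers of the report would rely on it to judge what zero events can show.

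**Working it through.** **Inputs.** x = 0 events, n = 9, 95% with two limits (Section 11.1). Cohort 2 is 12 at 3:1 active to placebo in each blinded period (Sections 5.1 and 5.2, Table 6). Cohorts 1 and 3-6 are 10 each at 4:1.

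**Trying to reproduce 0.04 to 0.39.** The 95% intervals for 0 of 9 are:

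| Method | Lower | Upper |
|---|---|---|
| Clopper-Pearson (exact) | 0 | 0.336 |
| Wilson | 0 | 0.299 |
| Wilson, continuity-corrected | 0 | 0.371 |
| Agresti-Coull | -0.045 (cut to 0) | 0.345 |
| Plus-four | -0.042 (cut to 0) | 0.350 |
| Jeffreys | 0.00005 | 0.238 |
| Bayesian, uniform prior: Beta(1,10) | 0.003 | 0.308 |

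None gives the stated pair. Two partial matches exist: plus-four has a lower limit of -0.042, which is 0.04 if the sign is lost, and a 97.5% exact interval has an upper limit of 0.386. They come from different methods and different coverage. The exact 95% interval for 1 of 9 (0.003 to 0.482) does not fit either.

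One calculation does match both limits to two decimals. A uniform prior with **one** event in 9 gives Beta(2,9), whose 5th and 95th percentiles are 0.037 and 0.394. That is a 90% central interval for 1 of 9, not a 95% interval for 0 of 9.

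**Exact interval.** For x = 0 the lower limit is 0 and the upper limit is 1 - 0.025^(1/n).

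- n = 9 (Cohort 2 blinded doses): 1 - 0.025^(1/9) = 0.336
- n = 8 (Cohorts 1 and 3-6): 1 - 0.025^(1/8) = 0.369
- n = 12 (fed period, if all of Cohort 2 enter): 1 - 0.025^(1/12) = 0.265

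**Why 0.04 cannot be a lower limit.** P(0 of 9) = (1 - p)^9. At p = 0.01 this is 0.99^9 = 0.914. At p = 0.04 it is 0.96^9 = 0.693. Zero events is the likeliest result at both rates, so neither is implausible.

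**Counts.**

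| | Section 11.1 | Section 5.2 |
|---|---|---|
| Cohort 2 | 8 | 12 |
| Part A | 10 + 8 = 18 | 10 + 12 = 22 |
| Study, with 40 in Part B | 18 + 40 = 58 | 22 + 40 = 62 |
| Active per blinded Cohort 2 dose | 8 x 3/4 = 6 | 12 x 3/4 = 9 |

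The 9 on active in Section 11.1 therefore needs 12 in Cohort 2. In Cohort 1 and Part B, 10 x 4/5 = 8.

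**The case against.** **Origin of the figures.** The match to Beta(2,9) suggests that the authors may have meant a Bayesian interval for one event in nine, and the word certainty would suit that. It is a possible source only, since other inputs lead to the same distribution. It does not rescue the sentence: the text says 0 events and 95%, and the figures need 1 event and 90%. It is a reason for the sponsor to confirm which event count was meant.

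**A minimum is only a floor.** Section 11.1 calls 18 a minimum, and Section 5.1 lets Cohort 2 shrink to an open-label two-way food-effect comparison if the higher doses are not studied. A floor of 8 is therefore not logically impossible. But Section 5.2 also calls its 62 a minimum, with 12 in Cohort 2, and Section 11.1's own 9 on active fits only 12. Leftover text is the better reading.

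**Not the only stale count.** The dosing note in protocol Table 2, repeated in SAP Appendix 2, still refers to 6 participants remaining after the first 2, which implies 8 per dose level. It does not state a size for Cohort 2. It stands as a further count to reconcile.

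**The fed period.** The maximum of 9 can be read as meaning the blinded doses only. That is reasonable, but the sentence covers every active dose in both parts. The figure of 12 is itself the planned number: Section 5.2 allows up to 10 additional participants in a cohort.

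**Consequence.** This objection is the strongest, and it stands. The sample size rests on feasibility, no hypothesis is tested, safety is summarised descriptively, and neither Section 8 of the protocol nor any SAP display uses the interval. SAP Section 2.1 records that the study was terminated during Cohort 2. The upper limit, the one that matters for reassurance, errs on the cautious side.

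**Conclusion.** The concern holds on both parts. For 0 of 9, the stated 0.04 to 0.39 should be 0 to 0.336 by the exact method: 4 percentage points too high at the lower end and 5.4 at the upper. The size of the upper error depends on the method chosen, but every 95% method in the table puts the lower limit at or near 0 and the upper limit below 0.39. The interval treats the participants on a dose as independent with a common event probability.

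Cohort 2 is given as 8 in Section 11.1 against 12 in every other current passage that states its size, so the Part A minimum is 18 against 22.

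The effect is limited to what a reader learns from Section 11.1. It is worth correcting because that is the plan's only precision statement for its primary objective, and because neither the interval nor the count of 8 should pass into the study report.

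**What to change.** In protocol Section 11.1:

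1. Replace the interval sentence with wording such as: If 0 of 9 participants (Cohort 2 blinded doses) or 0 of 8 (Cohorts 1 and 3-6) on an active dose have a given event, the exact (Clopper-Pearson) two-sided 95% confidence interval for its probability is 0 to 0.34 or 0 to 0.37, respectively. Another valid method is acceptable if it is named. If the sponsor meant to illustrate one event, that should be a separate sentence with its own interval (exact 95% for 1 of 9: 0.003 to 0.482).
2. State that the maximum of 9 excludes the open-label fed period, which is planned for up to 12 (0 of 12: 0 to 0.26).
3. Change the Part A count to 22 (10 + 12), in line with Section 5.2.

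Reconcile the participant count in the Table 2 dosing note, and its copy in SAP Appendix 2, with the cohort sizes.

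The cost is a few sentences of wording. Sample size, design and analysis do not change. If the protocol will not be amended after termination, the same corrections belong in the study report wherever it cites Section 11.1.

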## 11.2. Populations for Analyses

For purposes of analysis, the following populations are defined:

Population	Description
Screened	
 
All participants who were screened for eligibility
 

Randomized	
 
All participants who were randomly assigned to treatment in the study.
 
This population will be based on the treatment the participant was randomized to.
 

Safety	
 
All randomized participants who received at least one dose of study treatment.
 
This population will be based on the treatment the participant actually received.
 
 
Note: Participants who were not randomized but received at least one dose of study treatment should be listed.

PK	
 
All participants in the Safety population who had at least 1 non-missing PK assessment (Non-quantifiable [NQ] values will be considered as non-missing values).
 
This population will be based on the treatment the participant actually received.
 

## 11.3. Statistical Analyses

### 11.3.1. Safety Analyses

All safety analyses will be performed on the Safety Population.

Endpoint	Statistical Analysis Methods
Primary	Will be presented in tabular and/or graphical format and summarised descriptively according to GSK's Integrated Data Standards Library standards.

### 11.3.2. PK Analyses

All pharmacokinetic analyses will be performed on the Pharmacokinetic Population.

For the secondary pharmacokinetic (PK) endpoints in this study, no formal hypotheses will be tested.

Endpoint	Statistical Analysis Methods
Secondary	
Plasma GSK2983559 and GSK2668176, concentration-time data will be analysed by non-compartmental methods. Calculations will be based on the actual sampling times recorded during the study.
 
From the plasma concentration-time data, the following pharmacokinetic parameters will be determined, as data permit: maximum observed plasma concentration (<math>C_{max}</math>), time to <math>C_{max}</math> (<math>t_{max}</math>), area under the plasma concentration-time curve [<math>AUC_{(0-24)}</math>, <math>AUC_{(0-t)}</math> and <math>AUC_{(0-\infty)}</math>], and apparent terminal phase half-life (<math>t_{1/2}</math>).
 
Part A (single dose): Dose proportionality will be assessed by visual inspection of dose normalised <math>AUC_{(0-\infty)}</math> [or if not available <math>AUC_{(0-t)}</math>] and <math>C_{max}</math> values versus dose. Analysis of these <math>\log_e</math>-transformed parameters may be carried out, using the power model.
 
Part A (food effect): The ratio of fed state to fasted state may be assessed for the <math>\log_e</math>-transformed parameters <math>AUC_{(0-\infty)}</math> [or if not available <math>AUC_{(0-t)}</math>] and <math>C_{max}</math>. The effect of food will be assessed utilising a mixed effects model, with fed state (fasted or fed) as a fixed effect and participant as a random effect.
 
Part B: The extent of accumulation after repeat dosing, the observed accumulation ratio (<math>R_o</math>), may be determined. The plasma steady state ratio (<math>R_s</math>) and an assessment of plasma steady state across the trough concentrations may also be made. Dose proportionality may be assessed using similar methods to the single dose Part A.
 
For combined 5-ABT and NAc-5-ABT (corrected to 5-ABT), observed <math>C_{max}</math> and <math>T_{max}</math> will be determined using non-compartmental methods and will be summarised descriptively.
 
Further details will be included in the RAP.

### 11.3.3. Other Analyses

Pharmacodynamic, and biomarker exploratory analyses will be described in the reporting and analysis plan. The population PK analysis and pharmacodynamic analyses will be presented separately from the main clinical study report (CSR).

### 11.3.4. Interim Analyses

Dose escalation meetings will occur after each period in Part A and after the completion of 14 days dosing of each cohort in Part B. The decision to proceed to the next cohort and next dose strength to be studied, will be made by DEC based on assessment of safety (e.g., AEs, clinical laboratory results, vital signs and ECG) and plasma GSK2983559 pharmacokinetic and 5-ABT concentrations obtained in all participants at the prior dose level. Individual safety data (adverse events, laboratory safety tests, ECGs and vital

signs) will be reviewed. This study is double blind (sponsor open), where the participant, investigator and site staff will remain blinded to the treatment allocation. Sponsor open refers only to those members of the DEC.

Following completion of Cohort 1 (Part A) and before starting Cohort 2 (Part A), a GSK internal safety board (independent of DEC) will be reviewing the data.

A formal interim analysis may be performed during the study on completed cohorts in Part A of the study to aid internal decision making only. Only the DEC members will be unblinded. There will be no changes to the study design or planned number of participants in future cohorts as a result of this interim analysis. This analysis may include review of individual participant data, summaries, graphical presentations and/or statistical analysis.

The Reporting and Analysis Plan will describe the planned interim analysis in greater detail.

## 13. APPENDICES

### 13.1. Appendix 1: Abbreviations and Trademarks

5-ABT	5-amino-benzothiazole
Abs.	Absorbance
ACN	Acetonitrile
AE	Adverse Event
ALT	Alanine Aminotransferase
API	Active Pharmaceutical Ingredient
AST	Aspartate Aminotransferase
AUC	Area Under the Concentration-time curve
AUC (0-24)	Area Under the Concentration-time curve from time zero to 24 hours post first dose
AUC (0-t)	Area Under the Concentration-time curve from time zero (pre-dose) to last time of quantifiable concentration within a subject across all treatments
AUC (0-τ)	AUC from 0 hours to the time of next dosing.
AUC (0-∞)	Area Under the Concentration-time curve from time zero to infinity
BID	Twice a Day
BMI	Body Mass Index
BP	Blood Pressure
BUN	Blood Urea Nitrogen
CARD	C-terminal Caspase-activation-and-recruitment
CD	Crohn's Disease
CFR	Code of Federal Regulations
CHMP	Committee for Medicinal Products for Human Use
CIOMS	Council for International Organizations of Medical Sciences
CKD-EPI	Chronic Kidney Disease Epidemiology Collaboration
CL/F	Apparent total clearance of the drug from plasma after oral administration
C max	Maximum Observed Concentration
CMC	Chemistry, Manufacturing and Controls
C min	Minimum Observed Concentration
CNS	Central Nervous System
CONSORT	Consolidated Standards of Reporting Trials
CPK	Creatine Phosphokinase
CPMP	Committee for Proprietary Medicinal Products
CRF	Case Report Form
CRP	C-Reactive Protein

CSR	Clinical Study Report
CTCAE	Common Terminology Criteria for Adverse Events
C trough	Trough concentration measured at the end of a dosing interval at steady state
DEC	Dose Escalation Committee
DLs	Dose Levels
DNA	Deoxyribonucleic Acid
ECG	Electrocardiogram
eCRF	Electronic Case Report Form
EDTA	Ethylenediaminetetraacetic Acid
EMA	European Medicines Agency
EMEA	Europe, the Middle East and Africa
FaSSIF	Fasted State Simulated Intestinal Fluid
FDA	Food and Drug Administration
FeSSIF	Fed State Simulated Intestinal Fluid
FSH	Follicle Stimulating Hormone
FTiH	First Time in Human
g	Gram
GCP	Good Clinical Practice
GCSP	Global Clinical Safety and Pharmacovigilance
GFR	Glomerular Filtration Rate
GI	Gastrointestinal Tract
GLDH	Glutamate Dehydrogenase
GLP	Good Laboratory Practice
GSK	GlaxoSmithKline
Haem.	Haematology
HBcAb	Hepatitis B Core Antibody
HBsAg	Hepatitis B Surface Antigen
hCG	Human Chorionic Gonadotropin
HIPAA	Health Insurance Portability and Accountability Act
HIV	Human Immunodeficiency Virus
HPLC	High Performance Liquid Chromatography
HPMC	Hydroxypropylmethyl Cellulose
HPMCAS	Hydroxypropylmethyl Cellulose Acetate Succinate
HR	Heart Rate
Hr/hrs/h	Hours
HRT	Hormonal replacement therapy
HWB	Human Whole Blood
IB	Investigator's Brochure
IC	Inhibitory Concentration

ICF	Informed Consent Form
ICH	The International Council for Harmonisation of Technical Requirements for Pharmaceuticals for Human Use
IgG	Immunoglobulin G
IgM	Immunoglobulin M
IL-	Interleukin
IMPD	Investigational Medicinal Product Dossier
INR	International Normalized Ratio
IP	Investigational Product
IRB/IEC	The Institutional Review Board/ Independent Ethics Committee
IRT	Interactive Response Technology
IUD	Intrauterine Device
IUS	Intrauterine Hormone-releasing System
Ka	Absorption Rate Constant
kcal	Kilocalorie
kg	Kilogram
L	Litre
LDH	Lactate Dehydrogenase
LLOQ	Lower Limit of Quantification
LRR	Leucine-rich Repeat
m 	Metre Squared
MABEL	Minimal Anticipated Biological Effect Level
MAPK	Mitogen-activated Protein Kinase
MDP	Muramyl Dipeptide
mg	Milligram
MHRA	Medicines and Healthcare Products Regulatory Agency
Min/mins	Minute
MIP1 $\alpha$	Macrophage Inflammatory Protein 1 Alpha
MIP1 $\beta$	Macrophage Inflammatory Protein 1 Beta
mL	Millilitre
MSDS	Material Safety Data Sheet
msec.	Millisecond
NAc-5-ABT	n-acetyl-5-amino benzothiazole
NCBP	Non-Child Bearing Potential
ng	Nanogram
nm	Nanometre
NOAEL	No Observable Adverse Effect Limit
NOD1	Nucleotide-binding Oligomerization Domain 1
NOD2	Nucleotide-binding Oligomerization Domain 2
NOEL	No Observable Effect Limit

NQ	Non-quantifiable
PBPK	Physiologically Based Pharmacokinetic Modelling
PD	Pharmacodynamic
PK	Pharmacokinetics
ppm	Parts Per Million
PR	Pulse Rate
PRRs	Pattern Recognition Receptors
QD	Once Daily
QTc	Electrocardiogram QT interval corrected for heart rate
QTcB	Electrocardiogram QT interval corrected for heart rate using Bazett's formula
QTcF	Electrocardiogram QT interval corrected for heart rate using Fridericia's formula
RAP	Reporting and Analysis Plan
RBC	Red Blood Cell
RIP2	Receptor Interacting Protein 2
RIPK2	Receptor-interacting Serine/Threonine Protein Kinase 2
RNA	Ribonucleic Acid
Ro	Accumulation Ratio
Rs	Steady State Ratio
SAE	Serious Adverse Event
SGOT	Serum Glutamic-Oxaloacetic Transaminase
SoA	Schedule of Activities
SPF	Sun Protection Factor
SRM	Study Reference Manual
SUSAR	Suspected Unexpected Serious Adverse Events
T 1/2	Half Life
TB	Tuberculosis
TE	Target Engagement
TK	Toxicokinetic
T max	Time taken to maximum observed plasma drug concentration
TNF	Tumour Necrosis Factor
TNF $\alpha$	Tumour Necrosis Factor Alpha
TTC	Threshold of Toxicological Concern
UC	Ulcerative Colitis
$\mu$ g	Microgram
$\mu$ g.h	Microgam per hour
UK	United Kingdom
ULN	Upper Limit of Normal
UVA/UVB	Ultraviolet A/Ultraviolet B

UV/VIS	Ultraviolet/Visible light
WOCBP	Woman of Child Bearing Potential

